### 2.2.5.5 Fidelity Assurance

We will follow recommendations for quality assurance in behavioral interventions. Use of standardized intervention materials, structured staff training and ongoing oversight are fundamental to ensuring high intervention fidelity. The lifestyle coach will undergo standardized training by a certified GLB master trainer with supplemental training on the cultural adaptations recommended by the Latino Patient Advisory Board. Per our standard practice, all group sessions will be audiotaped and a random 10% sample from the sessions by recruitment cohort will be audited and graded using a session-by-session rating scale from a previous trial. The coach will complete a checklist of critical intervention behaviors and materials delivered during each session. Self-monitoring records and Smartphone application communication are readily retrievable and will be reviewed as part of routine quality control efforts. Falling below an a priori performance standard (e.g., 90% adherence to intervention protocol) will trigger more

frequent audit and feedback and, if needed, “booster” training for the coach. Participant engagement and adherence are also essential to intervention fidelity and must be monitored and supported. Participant progress on key intervention tracking parameters (e.g., date, format, duration of contact, most current weight, and physical activity level) will be routinely documented. The coach will review and give feedback on homework and self-monitoring records and document participant progress toward protocol-specific, achievement-based objectives. The coach will routinely inquire about barriers to intervention receipt and adherence, recommend personalized, actionable problem-solving strategies, and provide ongoing support via proactive follow-up.

### 2.2.6 Participant Safety

PCP approval will be required before potentially eligible patients are contacted by the study team. Participants will be carefully screened and individuals for whom the interventions would be medically inappropriate or unsafe will be excluded. Participants who develop any exclusionary condition (e.g., diabetes) following randomization may continue with the interventions and follow-up assessments with their PCP’s approval. To ensure unbiased ascertainment between the intervention and control group, outcome assessors will systematically screen all participants for adverse events during in-person assessments at baseline and 18 months using a standard interview and reporting form as done in our previous trials. In addition, outcome assessors will call all participants at six and 12 months to screen for adverse events. Positive responses will trigger an adverse event record, which will be reviewed by the study clinician for seriousness, study relatedness, and expectedness. Similar information reported by participants at other times (e.g., during intervention encounters) will be duly noted and followed, as needed, to assure participant safety. Participants will be referred to their PCP for a medical evaluation as needed. We will report adverse events to the study safety officer.

A study safety officer will review the original protocol and any subsequent amendments, perform expedited monitoring of serious adverse events (SAEs) that are unexpected and related, perform ongoing monitoring of drop-outs, all other SAE’s, and non-SAEs, determine whether study procedures should be changed or the study halted due to serious safety concerns and/or major problems with conduct of the study, and perform periodic review of the completeness and validity of data to be used for analysis of safety and efficacy. The study safety officer also will monitor implementation of procedures to ensure research participant privacy and data confidentiality.

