**Table 1. Inclusion and exclusion criteria**

---

Inclusion criteria:
 

• Age (as of date of enrollment):

○ Lower age limit: 18 years

○ Upper age limit: NONE (only exclude for cause, e.g. disease and functional limitations, as detailed below)

• Race/ethnicity: Latino of any race

• Gender: male

• Body mass index: <math>\geq 27</math> kg/m^2

• At least one cardiometabolic risk factor:

▪ Elevated waist circumference

▪ Elevated triglycerides

▪ Elevated blood pressure

▪ Elevated fasting plasma glucose

▪ Low high-density lipoprotein cholesterol

• Primary Care Provider approval of study contact

• Able and willing to enroll and provide informed consent, i.e., to meet the time and data collection requirements of the study, be randomized to one of two study arms, participate in follow-up for 24 months, and authorize extraction of relevant information from the EHR

 
Exclusion criteria:
 

• Medical exclusions:

○ Previous diagnosis of diabetes or diabetes diagnosed as a result of fasting blood glucose or hemoglobin A1c levels obtained through study screening;

○ Diagnosis of cancer (other than non-melanoma skin cancer) that is/was active or treated with radiation or chemotherapy within the past 2 years;

○ Inability to walk without the assistance of another person;

○ Severe medical co-morbidities that require aggressive treatment: e.g., stage 4 or greater renal disease, class III or greater heart failure, unstable coronary artery disease, liver or renal failure;

○ Diagnosis of a terminal illness and/or in hospice care;

○ Diagnosis of bipolar disorder or psychotic disorder within the last 2 years, or currently taking a mood stabilizer or antipsychotic medication

○ Initiation or change in type or dosing of antidepressant medications within 2 months prior to enrollment (The patient will be re-contacted for a later cohort once his/her regimen has been stable for at least 2 months unless the person declines to participate altogether.)

○ Have had or plan to undergo bariatric surgery during the study period

• Other exclusions:

○ Having no reliable telephone service

○ Plan to move out of the area during the study period

○ Family/household member of another study participant or of a study staff member

○ Investigator discretion for clinical safety or protocol adherence reasons

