### 2.2.7 Study Measures and Data Collection Schedule

Assessments will occur at baseline, 6, 12, and 18 months on clinical, behavioral, and psychosocial outcome measures and potential effect modifiers and mediators at one of the PAMF clinics from which participants are recruited (**Table 4**). Trained bilingual and bicultural research assistants blinded to participants’ random assignment will conduct assessments using standardized measurement protocols and equipment and previously validated interviewer-questionnaires (in-person or by phone). For in-person data collection, participant’s preferred time and location will be accommodated whenever possible, including evenings and weekends. We will also utilize self-administered questionnaires online, which we have shown to be acceptable and feasible in previous trials with Latinos. We will use Spanish or English as indicated by the participant.

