#### 2.2.7.1 Primary and Secondary Outcomes

The primary outcome is proportion of participants who sustain at least 5% of baseline weight loss at 18 months. Research assistants will weigh participants in duplicate using a standard

calibrated scale at baseline and 18 months at local clinic sites as in previous and ongoing trials. The primary outcome was selected based on its clinical relevance for patients, providers, and health care systems, as well as patient and stakeholder input. Weight loss of  $\geq 5\%$  of baseline weight is known to confer a reduction in risk of diabetes and other chronic disease. This outcome emphasizes chronic disease prevention by focusing on clinically relevant weight loss. Our patient advisors advocated for this primary outcome because their primary goal for the intervention is to reduce the risk for chronic disease. We will examine three types of secondary outcomes:

**Health behaviors** (dietary intake, physical activity, and sedentary behavior) and psychosocial well being will be collected via phone or online questionnaire at baseline, 6, 12, and 18 months (Aim 2). Dietary intake will be assessed using the gold-standard approach of multiple pass 24-hour recalls in Spanish or English by highly trained and experienced staff, over the phone, at baseline and 18 months. Physical activity and sedentary behavior will be assessed using the interviewer-administered 7-day Physical Activity Recall and a self-report measure of sedentary behavior over the phone at all time points. Participants will complete online questionnaires that we have successfully used in prior trials to assess psychosocial well-being (e.g., EuroQol EQ-5D, PHQ-9 for depression). If needed, a research assistant can help a participant fill out the online questionnaire at an office visit.

**Cardiometabolic risk factors** (blood pressure and waist circumference) measured at baseline and 18 months (Aim 2). Trained research assistants will conduct blood pressure and waist circumference measurement according to standard protocols. Waist circumference will be measured in duplicate at the right iliac crest, in centimeters as per previously published protocols.

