### 2.2.9 Statistical Analysis

#### 2.2.9.1 Analytical Plan

Aim 1 and 2: The primary hypothesis that HOMBRE will lead to a greater percentage of Latino men who sustain  $\geq 5\%$  of baseline weight loss through 18 months than the minimal intensity intervention control group will be tested with a generalized linear mixed model.

$$Y = \beta_0 + \beta_1 X + \beta_2 Y_0 + \sum \beta_{4+i} Z_i + \alpha + \gamma + e \quad (1)$$

Let  $Y$  be the outcome of interest for a patient randomized to arm  $X$  (HOMBRE or control). Given the covariate-adaptive randomization, distributions of baseline values on the outcome variable ( $Y_0$ ) and key characteristics ( $Z_i$ ) should be similar between study arms and thus not bias the results. But to the extent they are associated with the outcome, their inclusion in the analysis will account for otherwise unexplained variation and hence increase efficiency.  $\alpha$  and  $\gamma$  are clinic and PCP nested within clinic random effects, and  $e$  is the random error term. Aim 2 examining secondary outcomes at 18 can be evaluated by adapting the same model. The outcome variables in Aim 2 (e.g., cardiometabolic, health behavior, and psychosocial well-being indicators) will be continuous. We will model the change from baseline in each indicator as the outcome  $Y$  and the fixed and random effects will remain the same as described in model (1).

Primary analyses will follow intent to treat principles. We will verify that mixed model-based results are not sensitive to violations of model assumptions with permutation and bootstrap resampling tests. We will document the extent, pattern, and reasons for missing data, and will conduct sensitivity analyses of the impact of missing data on stability of the primary results. For example, we may use weight data up to the point when they are no longer available (e.g., dropouts) or should not be used, and then employ multiple imputation based on a predictive distribution for future weights.

Exploratory Aim 1: Weight loss trajectories using weight data from the EHR will be examined using tests of group-by-time interactions in mixed-effects growth curve model.

$$Y_t = \beta_0 + \beta_1 X + \beta_2 Y_0 + (\beta_3 + \beta_4 X) T + \sum \beta_{4+i} Z_i + \alpha + \gamma + b_0 + b_1 T + \varepsilon \quad (2)$$

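### Once a man develops an exclusionary condition, follow-up assessments as well as the intervention depend on PCP approval; this is not reconciled with screening all participants and can cost the 18-month primary weight

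*Combined protocol and SAP*

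**What the plan says.** Section 2.2.6 (Participant Safety) gives the rule for a condition arising after randomisation: "Participants who develop any exclusionary condition (e.g., diabetes) following randomization may continue with the interventions and follow-up assessments with their PCP’s approval". One approval covers both activities. The section does not say what happens to data collection if approval is refused or never given.

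The same section then describes safety ascertainment without any such condition: "outcome assessors will systematically screen all participants for adverse events during in-person assessments at baseline and 18 months", and "outcome assessors will call all participants at six and 12 months to screen for adverse events".

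Section 2.2.7 defines the assessment schedule: "Assessments will occur at baseline, 6, 12, and 18 months on clinical, behavioral, and psychosocial outcome measures". Section 2.2.7.1 says the primary weight is taken by research staff on a "calibrated scale at baseline and 18 months at local clinic sites", and Table 4 shows no other in-person weight.

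Table 1 excludes at entry "Previous diagnosis of diabetes or diabetes diagnosed as a result of fasting blood glucose or hemoglobin A1c levels obtained through study screening", so diabetes, the rule's own example, is a listed condition. Section 2.2.9.1 says "Primary analyses will follow intent to treat principles".

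**The concern.** A weighing, a blood pressure reading, a questionnaire or an adverse-event interview does not expose a man to the intervention. Tying these to the same approval as the intervention allows follow-up to end for a reason that arises after randomisation and concerns the man's health.

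Two things are at stake. First, the 18-month visit carries both the primary weight and the in-person adverse-event screen, so one refusal can remove both. Second, the loss would probably not be random. The programme aims to prevent diabetes, and Section 2.2.7.1 itself links 5% weight loss to diabetes risk. Other Table 1 conditions, such as cancer or bariatric surgery, could plausibly go with large weight loss. The men lost could therefore be failures or successes on the primary outcome.

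The loss could also differ by arm. Section 2.2.3 lists the investigators, safety officer, outcome assessors and data analyst as masked. PCPs are not on that list, and the documents do not say whether they learn the allocation.

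**Working it through.** **Step 1: set the passages side by side.**

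- Approval rule (2.2.6): after a new exclusionary condition, follow-up assessments continue with PCP approval.
- Safety screens (2.2.6, following sentences): every participant, at 6, 12 and 18 months, with no exception.
- Assessments (2.2.7): 6, 12 and 18 months count as assessment times, so the approval rule can be read to cover all three.
- Primary weight (2.2.7.1, Table 4): measured by staff at baseline and 18 months only.

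Staff facing a refusal at 18 months have two instructions that point in opposite directions for the adverse-event screen. For the weight they have only the approval rule.

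**Step 2: is there a specified replacement for the weight?** EHR weights are abstracted to 24 months, but for trajectories (2.2.7.1, Exploratory Aim 1). Multiple imputation appears in 2.2.9.1 as an optional example within sensitivity analyses. Model (1) has a single 18-month outcome per man, so it has no intermediate research weight to draw on when that value is missing. Neither safeguard is named as the primary remedy.

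**Step 3: reproduce the plan's sample size.** Inputs from 2.2.10: 15-point difference, two-sided alpha 0.05, 80% power, 80% retention, 212 per arm. The control rate is given only as slightly below 39%; I assume 35%, so 35% v 50% with mean 0.425.

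n = [1.96 × √(2 × 0.425 × 0.575) + 0.8416 × √(0.35 × 0.65 + 0.50 × 0.50)]² / 0.15² = (1.370 + 0.582)² / 0.0225 ≈ 169.3, so 170 evaluable per arm. Then 170 / 0.80 = 212.5, so 213 against the stated 212. Control rates from 33% to 39% give 209 to 217. The plan's figure reproduces.

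**Step 4: power.** At 212 × 0.80 = 169.6 evaluable per arm, power is 80.1%. If a further 2%, 5% or 10% of randomised men (assumed values) lost the weight on top of the planned 20%, the evaluable numbers would be 165.4, 159.0 and 148.4 per arm, with power 79.1%, 77.5% and 74.6%. If the planned 20% already includes these men, power does not change.

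**Step 5: selective loss, illustration only.** Assume true rates of 35% and 50%, ignore all other dropout, and let a share d of an arm be lost. If the lost men are all failures, the observed rate is p / (1 − d); if all successes, (p − d) / (1 − d).

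| Lost, control | Lost, HOMBRE | Difference, all failures | Difference, all successes |
|---|---|---|---|
| 5% | 5% | 0.50/0.95 − 0.35/0.95 = 15.8 points | 0.45/0.95 − 0.30/0.95 = 15.8 points |
| 8% | 4% | 0.50/0.96 − 0.35/0.92 = 14.0 points | 0.46/0.96 − 0.27/0.92 = 18.6 points |
| 5% | 10% | 0.50/0.90 − 0.35/0.95 = 18.7 points | 0.40/0.90 − 0.30/0.95 = 12.9 points |

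Equal loss barely moves the difference. Unequal loss moves it by a few points in either direction. These are extreme cases, because every lost man is given the same outcome.

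**The case against.** The strongest reply is that the wording is permissive. It does not say that a refusal or silence ends data collection. The PCP has already approved study contact, and nothing in the documents suggests PCPs would object to a weighing or a telephone call. The more specific sentences on safety ascertainment include every participant. This stands in part: loss of the adverse-event screen is a possibility created by conflicting text and cannot be stated as fact.

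The trigger is also narrower than it first appears. Table 4 has no follow-up glucose or HbA1c, so some conditions would surface only at a scheduled screen. A condition first reported at the 18-month visit comes to light at the visit where the weight is taken. This lowers the likely frequency but leaves conditions diagnosed earlier in usual care.

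There are partial safeguards: EHR weights, which 2.2.7.1 reports agree closely with research weights; re-contact after missed visits (2.2.8); events reported at other times; safety-officer monitoring of drop-outs; and planned missing-data sensitivity analyses. They reduce the consequence. None is specified to replace the primary weight or the systematic screen.

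Three stronger readings are tempting but unsupported. A reader might infer that an antidepressant change during follow-up triggers the rule; Table 1 words that item as "Initiation or change in type or dosing of antidepressant medications within 2 months prior to enrollment", which ties it to entry. A reader might infer a direct breach of intent to treat; the rule neither reassigns men nor excludes them from analysis, so at most it creates missing data. A reader might infer that a known number of men would be lost; no rate of new conditions or of refusals is given.

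**Conclusion.** The concern holds as an unreconciled conflict within Section 2.2.6. If the approval condition is applied as written, a man whose PCP does not approve can lose the 18-month primary weight and possibly the systematic adverse-event screen, after a post-randomisation event related to weight. That is avoidable, potentially informative missing data. It sits poorly with the intent-to-treat aim without contradicting it outright.

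The size cannot be determined from the documents. Under the assumed losses in the table, the observed difference runs from 12.9 to 18.7 points against a true 15, so bias could favour either arm. The 212 per arm is not called into question. The conclusion rests on reading follow-up assessments to include the 18-month visit, which Section 2.2.7 supports, and on some PCPs not approving, for which there is no frequency. The change is worth making because it is cheap; the text does not show that losses would be common.

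**What to change.** Reconcile the sentences in Section 2.2.6:

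1. Limit the PCP-approval condition to continuing the intervention, on whatever terms the sponsor decides. This review takes no position on those terms.
2. State that the 6-, 12- and 18-month adverse-event screens and the 18-month weighing continue for every randomised man, whatever the new condition or the PCP's decision about the intervention, unless he withdraws consent for follow-up.
3. Record the condition, its date and the PCP's decision, and report them by arm.

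The cost is a sentence or two in the protocol, a matching instruction to staff and a few data fields. No visits are added, since all these assessments are already scheduled. The downside is that some ill men may find the 18-month visit a burden; they remain free to decline.

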Implementation success during intervention delivery ( staff perspective )	Surveys of lifestyle coach: perceptions of (1) consistency of intervention procedures with available evidence, (2) intervention suitability for primary care, and (3) experience with the strategies facilitating intervention delivery based on the Promoting Action on Research Implementation in Health Services model. 	Interviews with lifestyle coach, PCPs, and clinic leadership: Barriers and enablers of delivering the intervention and differences across participating clinics, modifications to maximize implementation success?
Implementation success during intervention delivery ( patient perspective )	We will assess intervention participants' engagement and adherence by monitoring the number of group sessions attended, reasons for missed sessions, secure messaging and self-monitoring frequency, and adherence across participant subgroups.	Interviews with a random sample of participants: Relevance and acceptability of knowledge and skills, frequency of practicing intervention strategies, perceived benefits, problems encountered, cultural congruence, satisfaction with program format, materials, and coach performance?
Maintenance of intervention effects in individuals and settings over time	We will assess attrition and adverse events by participant characteristics and treatment condition.	Interviews with lifestyle coach, PCPs, and clinic leadership: Potential for integration into regular care and sustained, resources, policies, and care process redesigns needed to maximize sustainability.

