#### 2.2.10 Sample Size and Data interpretation

This trial is powered on the primary outcome of percentage of participants achieving  $\geq 5\%$  weight loss at 18 months. A sample of 212 participants/arm has 80% power to detect a difference of 15 percentage points between the HOMBRE intervention and control at  $\alpha=0.05$  (2-sided), assuming at least 80% retention at 18 months based on our prior trial experiences. We estimated that the percentage of men randomized to the minimal intensity intervention who would maintain clinically significant weight loss at 18 months would be slightly lower than what we observed in a prior trial (39%). Among racial/ethnic minorities, such as Latinos, lower proportions have maintained clinically significant weight loss in the intervention arms (e.g., 18% to 26%). Additionally, other low intensity interventions in primary care have also demonstrated a lower proportion maintaining clinically significant weight loss than what was observed in a prior trial. We chose a 15-point difference in percentage of men achieving  $\geq 5\%$  weight loss at 18 months based on our prior studies and other available literature. Among men randomized to the coach-led intervention in a prior trial, 51% maintained  $\geq 5\%$  weight loss at 24 months (12-point difference between groups). We anticipate a greater difference than observed in our prior trial, given that HOMBRE incorporates facilitated choice or delivery options and the control condition does not. The SHED-IT intervention tested a lower intensity intervention with a higher intensity intervention among Australian men over 12 months and found that 33% and 49% of men randomized to the respective arms maintained clinically significant weight loss (16 point difference).

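### Adverse events are actively sought only at 6, 12 and 18 months from men who can be reached; events after last contact have no planned source, and unscheduled reporting differs by arm.

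*Combined protocol and SAP*

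**What the plan says.** Section 2.2.6 (Participant Safety) sets the schedule. In person, "outcome assessors will systematically screen all participants for adverse events during in-person assessments at baseline and 18 months". By telephone, "In addition, outcome assessors will call all participants at six and 12 months to screen for adverse events". What opens a case is the man's own answer: "Positive responses will trigger an adverse event record, which will be reviewed by the study clinician for seriousness, study relatedness, and expectedness". Between screens, "Similar information reported by participants at other times (e.g., during intervention encounters) will be duly noted and followed, as needed".

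The same section asks the safety officer to "perform expedited monitoring of serious adverse events (SAEs) that are unexpected and related" and to "perform ongoing monitoring of drop-outs, all other SAE’s, and non-SAEs". It gives no time limit for the former and names no data source for the latter.

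Table 5 (section 2.2.7.3) plans the comparison: "We will assess attrition and adverse events by participant characteristics and treatment condition". It does not say which reports count or what the denominator is.

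Table 1 makes authorisation of EHR extraction, and willingness to be followed for 24 months, conditions of enrolment. The only EHR extraction described after randomisation is body weight, to 24 months (section 2.2.7.1 and Table 4). Before randomisation the EHR is also used to find eligible patients (section 2.2.2).

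**The concern.** Section 2.2.6 says its standard screen is there to keep ascertainment unbiased between arms. Two features work against that aim.

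First, the screen depends on reaching the man. One who leaves because of an injury or hospital stay may be among the hardest to interview, and nothing else is planned that would pick up his event once contact is lost.

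Second, the route that fills the gaps between screens is richer in one arm. If volunteered reports are added to screened ones, HOMBRE could appear to have more events simply because its coach-led men talk to staff more often.

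The two effects need not cancel, and the plan gives no way to separate them. A by-arm table could look reassuring because affected men were not asked, or look unfavourable to HOMBRE because its men were asked more often.

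**Working it through.** **Inputs.** 212 men per arm, 424 in total (sections 2.2.3, 2.2.10 and 4). Retention at 18 months: "assuming at least 80% retention at 18 months" (section 2.2.10). Retention in earlier trials of similar scope: 82%-92% (section 2.2.8). Scheduled screens at 0, 6, 12 and 18 months (section 2.2.6). Contact by arm from sections 2.2.5.3 and 2.2.5.4 and Table 3.

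**The plan's own figure.** This point does not depend on the sample size, but 80% retention is built into it. The plan does not state the exact control rate; it says slightly below 39%, and 33%-39% is assumed here. The pooled-variance formula for two proportions (15-point difference, two-sided 0.05, 80% power, no continuity correction), divided by 0.80, gives:
- Control 33%: 167 completers per arm, 167/0.80 = 209.
- Control 35%: 170 completers per arm, 170/0.80 = 212.5, rounded up to 213.
- Control 39%: 173 completers per arm, 173/0.80 = 217.

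The stated 212 is reproduced to within 3%.

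**Men without the 18-month screen** = 424 × (1 − retention).
- 80%: 424 × 0.20 = 84.8, about 85 (about 42 per arm if equal).
- 82%: 424 × 0.18 = 76.3, about 76.
- 92%: 424 × 0.08 = 33.9, about 34.

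**Time outside active screening.** Total time is 424 × 18 = 7,632 person-months. The documents do not say when men drop out, so three cases at 20% permanent loss are shown:
- Only the 18-month screen missed: 84.8 × 6 = 509, or 7%.
- Last contact spread evenly over months 0, 6 and 12: 84.8 × (18 + 12 + 6)/3 = 1,018, or 13%.
- All three post-baseline screens missed: 84.8 × 18 = 1,526, or 20%.

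**Detection delay.** Screens are 6 months apart. An event that nobody volunteers waits up to 6 months if the next screen is completed (mean 3 months if onset is uniform over the interval), and up to 12 months if one screen is missed.

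**Contact between screens, months 1-12, after the orientation session.**
- HOMBRE, in-person and videoconferencing: 12 weekly sessions plus a monthly call over months 4-12, so 12 + 9 = 21 scheduled conversations (22 if the section's count of 10 maintenance contacts is used).
- HOMBRE, self-directed: standardised messages; a coach if the man asks.
- Control: no scheduled coach contact; a coach if the man asks.

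No scheduled coach contact is described after month 12 in either arm, so this imbalance belongs to the first year.

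**What cannot be computed.** The documents give no adverse-event rate, no dropout rate by arm and no EHR capture rate. The number of events missed, the size of any skew and the number that the EHR would recover are unknown.

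**The case against.** The strongest defence is that section 2.2.6 is more complete than a bare reading of the visit schedule suggests. Unscheduled reports are accepted. Events recorded before a man leaves are kept. Section 2.2.8 has staff reschedule missed visits and re-engage men. The safety officer watches drop-outs and reviews data completeness, and Table 5 puts attrition beside adverse events. Screening is identically timed in both arms and done by blinded assessors. This is a low-burden behavioural trial with provider approval before contact.

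Most of that stands, and it rules out three stronger readings that a reader might infer:
- *The schedule contradicts expedited review.* It does not. In section 2.2.6 that term covers the handling of events already judged serious, unexpected and related; it promises no detection interval. The delay above is a limit on detection.
- *Drop-outs' events are all missing.* Only events after the last contact lack a planned source. The 85 is the upper end of the range, and many of those men may have answered at 6 and 12 months.
- *The EHR would close the gap.* Section 2.2.7.1 reports feasibility for weights only, and care outside the health system may not be recorded.

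The defence does not remove the remaining gap. The 80% allowance rests on earlier trials that already used such retention efforts. Oversight of drop-outs cannot reveal events that nobody collects. The unscheduled route is the one that differs by arm.

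**Conclusion.** The concern holds as a limit on ascertainment. Active screening after randomisation consists of three contacts that depend on reaching the man. At the planned minimum retention, up to about 85 of 424 men lack the last one (about 34 to 76 at earlier trials' retention), and 7% to 20% of person-months fall outside active screening, depending on when the 20% are lost. The unscheduled route gives coach-led HOMBRE men about 21 scheduled conversations in the first year, against none for control men. The by-arm comparison in Table 5 can therefore be incomplete, and can be skewed if the two kinds of report are pooled. Neither the direction nor the size of the net effect can be derived from the documents. Table 5 does not itself restrict the comparison to interviewed men; it leaves source and denominator unstated. The sample size and the primary analysis are unaffected.

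**What to change.** In sections 2.2.6 and 2.2.7.1, add hospitalisations, emergency visits and deaths to the EHR extraction planned for weights, for all 424 randomised men through 24 months. In Table 5, specify three things:
- EHR-identified serious events by randomised arm, shown beside events from the scheduled screens.
- Events volunteered at intervention encounters or at other unscheduled times, shown separately and not pooled with screened events.
- The number of men in each arm who completed each of the 6-, 12- and 18-month screens.

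The cost is some programming, clinician review time and a few sentences of text. It adds no participant visits and leaves the sample size unchanged. The sponsor should confirm that the EHR authorisation covers these fields and state how completely the system records them, since outside care will be captured incompletely in both arms. The EHR source depends on neither coach contact nor attendance at study visits, but it supplements the interviews and does not replace them.

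A periodic EHR safety query while the trial runs is optional. It could shorten detection for some events, but a delay as long as the query interval would remain and it needs repeated review time.
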